Descriptive statistics including measures of central tendency, dispersion and appropriate visualization approaches (e.g., box plots and spaghetti plots) will be performed on each outcome variable for patients and hospitals. This will be done to ascertain distributional characteristics and ensure that the assumptions (e.g., normality) associated with the planned statistical procedures are met. When necessary, transformations will be performed. All analyses will be done using an intent-to-treat philosophy. Baseline characteristics (both patient and setting levels) will be compared between intervention and control groups and the relevant variables (e.g., age) that differ by group will be included as covariates in hypotheses testing. In particular, we will control for the variables that correlate with function and physical activity including sex, comorbidities and cognitive impairment. Linear mixed models (LMMs)¹⁷⁰ for longitudinal data (admission, discharge, 1, 6 and 12 months) will be used to assess the intervention effect on continuous outcomes (e.g., physical activity, function, and length of stay) accounting for clustering of patients that may occur within the same hospital and for correlations between repeated measurements of each patient. Generalized Linear Mixed Model (GLMM) analyses will be conducted to assess the effect of the intervention on count outcomes (e.g., falls) or binary outcomes (e.g., readmission or not). The fixed effects included in the models will be treatment group (FFC-AC-EIT versus EO), time (admission, discharge, 1, 6, and 12 months post discharge for patients depending on the time points when the effects are evaluated), groupby-time interaction term and the aforementioned relevant covariates, such as age, sex, race. staffing, hospital size etc., identified from the baseline analyses will be included in the mixed

model to adjust for their influences. Random effects will include hospitals and patients. The hypotheses will be tested by evaluating the interaction term for each outcome variable. For each hypothesis, exploratory analyses will be performed to assess model assumptions. Post-analysis diagnostic measures (e.g., residuals) will be explored to assess model fit. All tests will use a 5% significance level. The use of LMM will provide flexibility with regard to assumptions related to the covariance structure of the residuals and the presence of missing data for the repeated measures¹⁷¹. As secondary analyses, we will also consider three-way interactive effects among demographic variables of interest (e.g., sex, age), and treatment condition, and time to identify moderators of the treatment effects. All of the Research Nurse Facilitators are women so we do not anticipate an effect of sex on outcomes. Generalized estimating equation (GEE) models will be used to compare changes in hospital level measures (i.e., environments, policies) (Hypothesis 3) from baseline to 6,12, and 18 months as GEE is more robust than LMMs when the sample size is relatively small (n=12)¹⁷².

Missing data. In prior research we had a 5-40% rate of attrition at the patient level and 0% at the hospital level^{12,33}. If there is significant dropout, we will identify baseline characteristics that differ between persons or hospitals that drop out. Maximum likelihood methods will be used for primary analyses, which address non-informative dropout [missing at random (MAR)]. If "informative" dropout is present, we will consider sensitivity analyses that add these relevant baseline covariates to make the MAR assumption more plausible¹⁷³.

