Testing the Efficacy of FFC-AC-EIT in Patients with Alzheimer's Disease and Related Dementias

NCT04235374

Date: 1/20/2019

Protocol

Design: To achieve our Aims we will use a cluster randomized clinical trial randomizing hospitals to prevent treatment contamination that might occur if we randomized units or patients within units.

Sample and Setting: Twelve hospitals (six in Maryland and six in Pennsylvania) will be randomized to treatment (FFC-AC-EIT) or Education-Only (EO) using permuted-block randomization and 50 patients per hospital will be recruited (total 600 participants). The hypotheses for Aim 1 efficacy testing include: Patient level: **Hypothesis 1:** At discharge, hospitalized patients with ADRD on units in which FFC-AC-EIT is implemented will increase time in physical activity; maintain or improve function; perform more function focused care activities; have less incidence and severity of delirium; have less evidence of BPSD; have less pain; have fewer falls; have fewer tethers; and shorter length of stays compared to those exposed to EO; **Hypothesis 2:** Patients on units in which FFC-AC-EIT is implemented will maintain or increase time spent in physical activity; maintain or improve function; have less incidence and severity of delirium; have less evidence of BPSD; have less pain; and have fewer falls; fewer emergency room visits; fewer unplanned re-hospitalizations; and fewer new admissions to long term care at 1, 6 and 12 months post discharge when compared to those exposed to EO.

Randomization Plan: The level of engagement required for the intervention prevents random assignment at the patient level as patients could become aware of differential treatment within the same unit in the same hospital and there is the risk of carry-over of treatment by staff. Thus, after hospitals are recruited they will be randomized to cohort (See Study Timeline) and randomly assigned to treatment so that the hospital will receive either FFC-AC-EIT or EO. Random assignment will be completed by the statistician using SAS proc plan which allows for simultaneous randomization on multiple dimensions (time and hospitals). In prior research we noted no differences in implementation of function focused care based on facility related factors^{111,137}. We recognize, however, that hospital differences may exist and will be controlled for in the analysis (e.g.,bed size, ownership).

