Sample Size: Sample size calculation was based on prior research and our primary focus which is on physical activity and function 12,14,15,33,106. For primary patient level outcomes, function based on the Barthel Index resulted in a Cohen's d=.24, for physical activity the Cohen's d=.37, and for participation in function focused care by patients Cohen's d=.31. The impact on tethering, a secondary outcome, was noted to have a Cohen's d=.61. Given a two-tailed alpha of .05, an estimated intra-class correlation coefficient (ICC) between clusters (hospitals) of .02, a correlation coefficient between repeated measures of .60, and assuming even dispersion of means, a total sample of 360 patients will provide sufficient power (>.80) to detect a small effect size (d=.24)¹³⁸ in primary patient level outcomes. Our prior research showed an attrition rate of 5-40% over a 12- month period. Therefore, we anticipate that a total of 600 patients from 12 hospitals (50 patients per hospital) will be sufficient to demonstrate outcomes. With regard to hospital level outcomes, our prior work resulted in effect sizes of 0.9 for environment and policy changes 15,33,106,139. With the proposed sample size of 12 hospitals the statistical power for these measures will be adequate (.90 for both outcomes based on our analysis plan).

Settings: Hospitals will be invited to participate if they: (a) have at least one unit dedicated to general medical patients; (b) identify two registered nurses (RN) to be champions (one for day and one for evening shifts); (c) enable staff to access email and websites via a phone, tablet or

computer; and (d) do not have a geriatric program (e.g., Acute Care for Elders, Hospital for Elder Life Program/ HELP) on the study units. We will implement FFC-AC-EIT in 6 hospitals (on the medical unit) and EO in 6 hospitals (on the medical unit) across Maryland and Pennsylvania. (See support letters and Facilities and Resources section).

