Education Only (EO) Control Intervention: Hospitals randomized to EO will be provided with an in-service for nursing staff on function focused care in patients with ADRD by an EO Research Nurse Facilitator using our developed PowerPoint presentations in 30-minute sessions as is currently done in usual practice. We will provide the education in the preferred format (e.g., face-to-face; webinar). No further interaction with the staff or the units will occur. We recognize that there will be differences in time exposure to the Research Nurse Facilitators but we are deliberately testing two different approaches to implementation of function focused care on hospital units with older adults with ADRD (FFC-AC-EIT versus EO). Time/exposure to the Research Nurse Facilitators is part of the approach and we will consider exposure time differences between the treatments.

Hospital descriptive data: The following data will be obtained at baseline to describe the hospitals and consider confounders: state; bed size; ownership status; urban or rural; Magnet[™] Status; teaching status.

Unit descriptive data: We will obtain staff/patient ratios and mix (registered, licensed practical nurses, and nursing assistants) at baseline, 6, 12 and 18 months and bed size.

Patient descriptive data: Data will include age, race, sex, cognitive status based on the MoCA^{140,141}, marital status, education, admission diagnosis, admission living situation, the Cumulative Illness Rating Scale (CIRS)¹⁵⁴, medications, length of stay, and discharge location and living location at each follow up period.

Measures for Aim 1 (Appendix A): Bolded measures are based on subjective data from informants (nurse/family); other measures are completed by evaluators based on observation or

chart abstracting. Environment and policy assessments are completed by evaluators who are blind to randomization.

Efficacy Data (see hypotheses 1-5 above):

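### Hospital-level covariates chosen because they differ by arm, from an uncapped list with 12 hospitals, risk precision for outcomes without an admission value and gain nothing elsewhere

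*Combined protocol and SAP*

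**What the plan says.** Three places bear on hospital-level adjustment.

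- Randomization Plan: "hospital differences may exist and will be controlled for in the analysis (e.g.,bed size, ownership"), so two variables are named as examples.
- Hospital descriptive data: items are collected to "describe the hospitals and consider confounders: state; bed size; ownership status; urban or rural", followed by Magnet and teaching status. That makes six. The unit descriptive data add staff/patient ratio, staff mix and unit bed size, for nine candidates in all.
- Data Analysis, Efficacy: patient and setting characteristics are compared between arms at baseline, and those that differ become covariates. The text then lists "staffing, hospital size etc., identified from the baseline analyses will be included in the mixed" model.

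The covariates enter as fixed effects, with hospitals and patients as random effects. Each hypothesis is tested by the group-by-time interaction. Length of stay is listed among the linear mixed model outcomes. The number of hospital covariates is not fixed, and no denominator-df method is named.

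**The concern.** Treatment is assigned to hospitals, so a direct comparison of arms rests on 12 units and 12 − 2 = 10 df. Each hospital-level term takes one df and, with so few units, is correlated with arm by chance. Selecting variables because they differ by arm favours those most collinear with treatment, whether or not they predict the outcome. The estimate then depends on which hospital descriptors happened to be unbalanced, and its interval may be wider than without adjustment. At stake are several named hypotheses: length of stay, emergency visits, unplanned re-hospitalisations and new long-term-care admissions.

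**Working it through.** **Inputs.** Sample Size section: "Given a two-tailed alpha of .05", "an estimated intra-class correlation coefficient (ICC) between clusters (hospitals) of .02" and "a correlation coefficient between repeated measures of .60". Sample and Setting: 12 hospitals with 50 patients each. With 360 patients retained, 360/12 = 30 per hospital.

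**The plan's own figure.** The section states that "a total sample of 360 patients will provide sufficient power (>.80) to detect a small effect size (d=.24"), "assuming even dispersion of means". Take a linear group-by-time contrast over five equally spaced visits scaled 0 to 1, with sum of squares .625 and residual variance 1 − .60 = .40. Then SE = √(4/360 × .40/.625) = .0843, and .24/.0843 − 1.96 = .886, so power is .81. Also 360/(1 − .40) = 600. The figure reproduces for a contrast in which the hospital intercept cancels.

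**Outcomes measured from admission.** A hospital main effect that is constant over time also cancels from change within patients. For illustration, take 20 patients per hospital (240 in all). The SE of the arm difference in change from admission to 12 months is √(4/240 × 2 × .40) = .1155. Generalised least squares for the planned model gives .1155 with 0, 1, 3, 4 or 6 hospital covariates, and .1388 to .1391 with 40% dropout. By contrast, the SE of the arm difference at a single visit rises from .152 with no covariates to .157 (1), .180 (3), .197 (4) and .232 (6) when they explain nothing.

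**Outcomes without an admission value.** With k hospital terms, the expected interval width relative to none is

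t(.975, 10 − k)/t(.975, 10) × √(9/(9 − k)) × √(1 − s).

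Here 9/(9 − k) is the expected variance inflation, (n − 3)/(n − 3 − k) with n = 12, for normal covariates unrelated to arm except by chance. The term s is the share of hospital-mean variance explained. It cannot exceed ICC/(ICC + (1 − ICC)/m):

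- m = 50: .02/(.02 + .98/50) = .505
- m = 30: .02/(.02 + .98/30) = .380

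Example, k = 4 and s = 0: 2.447/2.228 × √(9/5) = 1.47. In the best case at m = 50: 1.47 × √(1 − .505) = 1.04.

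For selection by imbalance, nine independent normal candidates were simulated and the k with the largest arm differences kept. This is an assumption, because the plan gives no threshold. "Best" means that all between-hospital variance is explained.

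| k | Unrelated, s = 0 | Unrelated, best, m = 50 | Unrelated, best, m = 30 | Selected, s = 0 | Selected, best, m = 50 | Selected, best, m = 30 |
|---|---|---|---|---|---|---|
| 1 | 1.08 | .76 | .85 | 1.24 | .87 | .97 |
| 2 | 1.17 | .83 | .92 | 1.39 | .98 | 1.10 |
| 3 | 1.30 | .91 | 1.02 | 1.54 | 1.08 | 1.21 |
| 4 | 1.47 | 1.04 | 1.16 | 1.71 | 1.21 | 1.35 |

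**Break-even for unrelated covariates.** The share of between-hospital variance they must explain is 27% (m = 50) or 36% (m = 30) for one, and 54% or 72% for two. For three it is 81%, or more than 100%. For four it exceeds 100% at both sizes.

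**Sensitivity to the ICC.** At an assumed ICC of .05, break-even remains possible up to five covariates (m = 50) or four (m = 30). At .01 it is possible only up to two or one.

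**The case against.** The strongest reply is that the planned test escapes the problem. Each hypothesis is tested by group-by-time, and for function and physical activity that term is essentially untouched. This stands. A reader might infer that hospital adjustment weakens the main efficacy tests; the plan's model does not support that.

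A reader might also infer that any hospital covariate does net harm with 12 clusters. That fails too: one or two fixed in advance can narrow the interval if they are prognostic, and two is the number of examples in the Randomization Plan.

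Nor do the documents commit to entering every descriptor. They are collected to describe hospitals and consider confounding, bed size and hospital size may be the same variable, and only those identified at baseline enter. The ratios of 2.16 with six covariates and 3.03 with seven therefore describe a model that the plan does not specify.

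Finally, length of stay is known at discharge, so 12-month attrition does not apply and 50 per hospital is the right size for it. The threshold there is four unselected terms, not three.

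What the reply does not remove is the selection rule. It is stated, it has no cap, and it favours collinearity with arm. For outcomes without an admission value, there is no change from admission for the interaction to test.

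**Conclusion.** The concern holds in limited form. For function and physical activity the hospital adjustment is close to neutral: exactly so in the balanced linear model, approximately under dropout or in a generalised linear mixed model. For outcomes that reduce to a between-hospital contrast, choosing covariates by imbalance widens the expected interval by about 24% with one and 39% with two if they explain nothing, against 8% and 17% for covariates unrelated to arm. At ICC .02, even complete explanation of between-hospital variance gives an expected net loss from four unselected terms at 50 patients per hospital or three at 30. With selection it starts at three and two. A larger ICC raises these thresholds.

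The figures assume hospital-level df, one term per covariate, and independent normal covariates; for count and binary outcomes they are approximate. If the software used residual df instead, part of the loss would appear as undercoverage rather than a wider interval. How many covariates would enter is unknown, and that openness is part of the defect.

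**What to change.** In Data Analysis, Efficacy:

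1. Delete the selection of hospital-level covariates by baseline difference.
2. Pre-specify at most one or two hospital covariates on prognostic grounds, for example bed size. Count any df used by randomisation strata. The documents mention permuted blocks and cohorts but do not say whether cohort is the block or how many cohorts there are, so this must be stated first.
3. Name a small-sample denominator-df method for the mixed models.
4. Move the remaining hospital and unit descriptors to sensitivity analyses, one at a time.
5. Align the sentence on hospital differences in the Randomization Plan with this list.

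The cost is wording only. The downside is that chance imbalances in the other descriptors are examined in sensitivity analyses rather than adjusted for in the primary model.

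### The group-by-time interaction alone cannot show benefit at each of 1, 6 and 12 months; Hypotheses 1 and 2 need named contrasts at each visit

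*Combined protocol and SAP*

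**What the plan says.** All references are to the combined protocol and SAP.

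- **Sample and Setting.** Hypothesis 1 concerns the patient's state at discharge. Hypothesis 2 is a separate list of post-discharge benefits, ending "fewer new admissions to long term care at 1, 6 and 12 months post discharge when compared to those exposed to EO".
- **Data Analysis, Efficacy (model).** "Linear mixed models (LMMs)¹⁷⁰ for longitudinal data (admission, discharge, 1, 6 and 12 months) will be used to assess the intervention effect on continuous outcomes". The fixed effects are group, time, their interaction and covariates. The visit list carries a qualifier: "for patients depending on the time points when the effects are evaluated". The random effects are hospital and patient.
- **Data Analysis, Efficacy (decision rule).** "The hypotheses will be tested by evaluating the interaction term for each outcome variable", and "All tests will use a 5% significance level".

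The section does not say whether time is categorical or continuous. It names no contrast at any visit and no order of testing, and it gives no rule for when a benefit at the three follow-up times counts as shown.

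The point applies to outcomes that have an admission value and are followed to 12 months: Barthel Index, Physical Activity Survey, NPI-Q, PAINAD and delirium severity. It does not apply to the MotionWatch 8 or the Patient Checklist for Function Focused Care, which are collected only in hospital.

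**The concern.** With time as a set of visits, the null hypothesis of the interaction is that the arms change equally across all visits in the model. Rejecting it says that they differ somewhere. It does not say at which visit, and the test has no sign. Hypotheses 1 and 2 are claims about particular visits and a particular direction.

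What is at stake is the content of Hypothesis 2. The programme is delivered on the hospital unit, and Hypothesis 2 asks whether benefit lasts after discharge. Under the stated rule, a benefit that fades early and one that lasts 12 months can give the same positive result. This affects function and physical activity, on which the sample size is based.

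**Working it through.** **Inputs from Sample Size.** "Given a two-tailed alpha of .05"; repeated-measures correlation ρ=.60; hospital ICC .02; 12 hospitals, 600 patients enrolled, 360 needed for analysis; "function based on the Barthel Index resulted in a Cohen's d=.24, for physical activity the Cohen's d=.37".

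**Assumptions added here.** Compound symmetry; a hospital effect constant over time, so that it cancels from the interaction; an effect at one visit only. Where dropout is used, retention is 100%, 100%, 90%, 75% and 60% at the five visits; the last figure is the worst attrition that the plan quotes.

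**Formula.** For the interaction over T visits with arm differences δ_t, the Wald statistic has T−1 df and noncentrality

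ncp = (N/4)/(1−ρ) × Σ(δ_t − mean δ)².

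If one visit alone differs by d, the sum is d²(1−1/T).

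**The plan's own figure.** Take differences rising evenly from 0 to .24 over five visits (0, .06, .12, .18, .24). The sum of squares about .12 is .036. At N=360, ncp = (90/.40) × .036 = 8.1. On 1 df the power is .81, which agrees with the plan's power above .80. On 4 df it is .61. Dividing 360 by .60 gives 600. So the sample size is reproducible, as a 1-df test.

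**Reading A: one five-visit model, 4 df, effect at discharge only.**

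| d | N | ncp | P(reject) |
|---|---|---|---|
| .24 | 600 | 375 × .0576 × .8 = 17.28 | .933 |
| .24 | 360 | 225 × .0576 × .8 = 10.37 | .734 |
| .37 | 600 | 375 × .1369 × .8 = 41.07 | >.99 |
| .37 | 360 | 225 × .1369 × .8 = 24.64 | .988 |

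With the assumed dropout, the .933 becomes about .91.

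Now take d=.24 sustained at all four visits after admission. The mean difference is .8d and the sum is d²(.64 + 4 × .04) = .8d². That is the same ncp, 17.28, and the same .933. Reversing the sign of every difference also leaves ncp unchanged. The test cannot tell an effect gone by 1 month from one that lasts a year, or benefit from harm.

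**Reading B: Hypothesis 2 model with admission, 1, 6 and 12 months, 3 df.** An effect at discharge only rejects at 5%. For an effect at 1 month only (d=.24), ncp = 375 × .0576 × .75 = 16.2 at N=600, giving .937 (about .89 with dropout). At N=360, ncp = 225 × .0576 × .75 = 9.72, giving .748.

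**Sensitivity (Reading A, discharge only, d=.24, N=600).**

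- ρ from .4 to .7: .78 to .98.
- F test with 40 or 10 denominator df: .90 or .76.
- Hospital-by-time variance up to .02, if modelled: down to .39. Under the plan's stated random effects the rate stays at .91 to .93.
- Time linear in months: .38 (.23 for an effect at 1 month only), with a negative slope.

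**With named contrasts instead.** Without dropout, each change-from-admission contrast has variance 4(1−ρ)/(N/2) = 1.6/300 and SE .073 at N=600.

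- Effect at discharge only: each follow-up contrast rejects 5% of the time, at least one of the three (unadjusted) 12.5%, all three 0.3%.
- Effect at 1 month only: the 1-month contrast rejects 91% of the time, the 6- and 12-month contrasts 5% each.
- A joint 3-df test of the three follow-up contrasts would not help in the second case: it rejects 94% of the time.

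**The case against.** **The five-visit reading is not certain.** The qualifier on the visit list can mean separate visit sets for each hypothesis. Hypothesis 1 would then be tested on admission and discharge, already a 1-df contrast, and a discharge-only effect would trigger Hypothesis 2 at 5%. The qualifier can equally refer to outcomes collected only in hospital. This objection stands: the discharge-only figures are conditional on Reading A.

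**A rejection for a 1-month effect need not be an error.** If the Hypothesis 2 null is no difference at any of the three months, a real 1-month difference makes it false and rejection is right. This also stands. The fault is narrower: the rejection does not support a claim at 6 or 12 months, and the plan does not say which of these nulls it means.

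**The omnibus test is inferred.** Evaluating the interaction could mean reading the individual group-by-visit coefficients, and the power figure fits a 1-df test better. That is possible, but the plan does not say so, and three such coefficients would still need a multiplicity rule.

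**The scenarios are chosen.** A full design effect at exactly one visit is an assumption; the sample size paragraph assumes evenly dispersed means. The rates show what the test cannot distinguish. They are not forecasts.

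A reader might infer that the plan has a type I error many times 5%, or that the sponsor will report a transient effect as lasting 12 months. The documents support neither. The rates are power against an interaction that is truly non-zero, and no text says how a significant interaction will be worded.

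**Conclusion.** The concern holds in a limited form. For outcomes with an admission value and follow-up to 12 months, the stated rule does not match the claims. With categorical time, on either reading of the visit list, a significant interaction cannot by itself support benefit at each of 1, 6 and 12 months. For d=.24 and 600 patients, a single-visit effect that leaves later months unaffected rejects about 93% of the time (discharge only, five-visit model) or 94% (1 month only, four-visit model). With the assumed dropout the figures are about 91% and 89%; with 360 patients and no dropout, 73% and 75%. They rest on ρ=.60, compound symmetry, no hospital-by-time variance and an effect at one visit only, and they are lower if time is linear.

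The text is ambiguous on the visit sets, so it does not establish that a discharge-only effect would be credited to Hypothesis 2. Nor is the sample size shown to be wrong. This is a cheap improvement to the test specification.

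**What to change.** Keep the five-visit model, so that discharge data still inform missing follow-up. For outcomes with an admission value, replace the sentence on testing the interaction with:

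- **Hypothesis 1:** arm difference in change from admission to discharge (1 df).
- **Hypothesis 2:** arm differences in change from admission to 1, 6 and 12 months, each 1 df with estimate, direction and 95% CI.
- **Multiplicity:** a prespecified rule for the three Hypothesis 2 contrasts, of the sponsor's choice, for example Holm or a stated fixed order.
- **Claims:** limited to the months that reject. The omnibus interaction becomes descriptive.

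The plan should also state that time is categorical.

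**Cost.** Wording and contrast statements in the same model, with no new data or patients. The real price is that a 12-month claim must be earned at 12 months. For a sustained d=.24 with 600 patients and the assumed dropout (40% lost by 12 months), the 12-month contrast has SE about .087, so d/SE = .24/.087 = 2.76 and unadjusted power is about .79. Under a fixed 1-6-12 order, the chance of reaching and passing the 12-month test is about .66, and a benefit that appears only at 12 months would be claimed less than 1% of the time. That is a reason to weigh the order before adopting it. The omnibus test has about .91, but it does not establish a 12-month effect.

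### The GEE for the two hospital-level scores is justified by the small sample, yet with 6 hospitals per arm an uncorrected robust test does not hold 5%, and no small-sample correction or reference distribution is named

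*Combined protocol and SAP*

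**What the plan says.** Data Analysis (Efficacy) states: "Generalized estimating equation (GEE) models will be used to compare changes in hospital level measures", meaning the environment and policy scores, with follow-up at 6, 12 and 18 months. The only reason given is "as GEE is more robust than LMMs when the sample size is relatively small (n=12". The same section sets the level, "All tests will use a 5% significance level", and says that each hypothesis is judged on the group-by-time interaction for the outcome concerned. That sentence stands among the mixed-model text and is not repeated for the GEE.

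The Settings paragraph gives the allocation: "We will implement FFC-AC-EIT in 6 hospitals (on the medical unit) and EO in 6 hospitals". The Missing data paragraph reports earlier experience of "5-40% rate of attrition at the patient level and 0% at the hospital level". The Sample Size paragraph quotes a hospital-level effect size of 0.9 and says "the statistical power for these measures will be adequate (.90 for both outcomes based on our analysis plan".

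Nowhere do the documents give, for this GEE, the working correlation, the variance estimator, a small-sample correction, the choice of Wald or score test, or the degrees of freedom. They also do not say whether time is a four-level factor or a trend.

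**The concern.** GEE tolerates a wrong working covariance because its standard errors come from the sandwich estimator. That estimator is justified by a large number of independent units, and here there are 12. The small sample is therefore a reason to correct the GEE test. The plan gives it as a reason for choosing GEE and then adds no correction. An analyst who follows the stated rationale would naturally use the robust variance, and in most software that comes with a normal or chi-square reference unless another is requested.

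At stake is the chance of a false claim that the intervention changed the hospital environment or policies. Because the plan's wording admits several tests with very different error rates, the stated 5% level is not secured for these two outcomes.

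**Working it through.** **Inputs.** From the documents: 6 v 6 hospitals; four occasions (baseline, 6, 12 and 18 months), hence three arm-by-time contrasts if time is a factor; 5% level; no hospital attrition in earlier work. Assumed: two-sided testing (stated only for the patient-level calculation), complete data, an arm-by-time cell-means model, normal scores, and no time-varying covariates.

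**The plan's own figure.** The only calculated hospital-level figure is power of .90. A plain 6 v 6 comparison at d = 0.9 gives 34% (z) or 29% (t). A repeated-measures interaction with f = .45 gives 89.6% with three occasions and correlation .5, but 98% with the planned four occasions and correlation .60. So .90 can be reached, but only with inputs the documents do not state. It is neither confirmed nor refuted.

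**Bias of the uncorrected sandwich.** In this balanced model it divides each arm's sum of squares by 6 × 6 = 36, where the unbiased variance of a mean uses 6 × 5 = 30. It is therefore 30/36 = 5/6 of the unbiased variance.

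**One contrast, uncorrected Wald.** The test rejects when |t(10)| > 1.96 × √(5/6) = 1.789. Type I error = 2 × P(t(10) > 1.789) = 10.4%; coverage 89.6%. The correct critical value is 2.228, so the intervals are 1.789/2.228 = 0.80 of the proper width.

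**Joint 3-df interaction, uncorrected Wald against chi-square.** With p = 3 and 10 df, Hotelling's T² × 8/30 follows F(3,8). Type I error = P(F(3,8) > 7.815 × (5/6) × (8/30)) = P(F(3,8) > 1.737) = 23.7%.

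**Any of three uncorrected contrasts significant.** By simulation, 22-25%, depending on the correlation pattern.

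**Sensitivity.** Simulation with hospital-level correlation of .3 to .9, exchangeable or AR(1), gives 10.2-10.5% (single) and 23.5-23.7% (joint). Bounded 0-18 and 0-15 sum scores give 10.0-10.5% and 22.9-23.5%. GEE fits in standard software agree.

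**Other tests the wording allows.**

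| Test | Single contrast | Joint 3 df |
|---|---|---|
| Score test | 5.5% | 3.1% |
| Model-based, exchangeable working correlation correct (rho .60 assumed) | about 4-5% | about 5-6.5% |
| Kauermann-Carroll, z or chi-square | 7.8% | 18.1% |
| Mancl-DeRouen, z or chi-square | 5.7% | 13.3% |
| Kauermann-Carroll, t(10) or scaled F(3,8) | 5.0% | 5.0% |

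The model-based variance depends on the working correlation. Suppose the truth is AR(1) with rho .60 and the working correlation is exchangeable. The average off-diagonal correlation is (3 × .6 + 2 × .36 + .216)/6 = .456, so the model takes every change to have variance 2(1 − .456) = 1.088. The true variances are 0.80, 1.28 and 1.568 for 6, 12 and 18 months. Dividing 1.96 by the square root of each ratio (0.735, 1.176, 1.441) gives effective cut-offs of 2.29, 1.81 and 1.63, that is 2.2%, 7.1% and 10.3%. Simulation gives roughly 2-3%, 7% and 10.5%.

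**Correcting the variance does not settle multiplicity.** Kauermann-Carroll with t(10) on all three contrasts, unadjusted, still gives 11-13% for at least one false positive.

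**The case against.** The strongest reply is that this is under-specification and not a demonstrated error. A reader might infer that the plan will run at 10% or 24%. The documents do not support that: they never say that an uncorrected robust Wald test will be used, and the score test or a well-specified model-based variance would stay close to 5% or below. This stands, and the error rates must be read as conditional.

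A reader might also infer that GEE is the wrong choice and that a mixed model would be better. That does not follow either. The plan's sentence is comparative, and the source it cites cannot be examined here. In simulation, a random-intercept model fitted by maximum likelihood with a z reference gave 14.7% for the 18-month contrast under AR(1) truth, against 10.4% for robust GEE. It did better under exchangeable truth (8.4%) and on the joint test (11-13% against 24%). The rationale is incomplete rather than false, so it needs qualifying, not deleting.

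The interaction sentence in Data Analysis favours one test per outcome over three separate ones. If time is a factor, that is the joint test, where the uncorrected error is larger; if time is a linear trend, it is a single contrast. The text of Hypothesis 3 is not reproduced in the document, so the intended contrast cannot be settled from it.

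Finally, the hospital scores lie outside the stated primary focus on physical activity and function. That limits the consequence but does not remove it.

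**Conclusion.** The point holds in conditional form and should be fixed. The stated reason for GEE points to the sandwich variance, and with 6 v 6 hospitals and no correction that route misses the 5% level: about twice nominal for a single contrast, and more than four times nominal for the joint chi-square test or for a claim based on any of three contrasts. Across the tests the wording permits, type I error runs from about 2% to about 25%.

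Confidence is high in the omission and in the 10.4% and 23.7% figures. They rest on balanced, complete data and barely depend on the hospital-level correlation or on the scores being bounded sums; losing one hospital (6 v 5) moves the single-contrast figure only to 11.0%. The model-based figures rest on an assumed rho of .60.

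A reader might further conclude that the .90 power is wrong. The documents do not show that. They show only that the figure is tied to an analysis plan that does not define the test.

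**What to change.** Keep GEE. Qualify the small-n rationale by adding that 12 hospitals require a small-sample correction, and name one test per outcome, consistent with the interaction-term sentence:

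- the joint 3-df arm-by-time interaction with the Kauermann-Carroll variance, the Wald statistic multiplied by 8/30 and referred to F(3,8); or
- one pre-named contrast with the Kauermann-Carroll variance and t(10). If all three contrasts are tested, add a multiplicity adjustment such as Holm.

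An equivalent exact small-sample method, such as a permutation test of hospital change scores, would also do. With bounded scores the corrected tests simulate at 4.5-5.1% (single) and 3.7-4.9% (joint).

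State whether covariates enter this GEE. Hospital characteristics fixed over time and entered as main effects leave the balanced contrast and its standard error unchanged. Time-varying ones do not, and nor do covariate-by-time terms. Staffing is such a variable: it is recorded as "staff/patient ratios and mix (registered, licensed practical nurses, and nursing assistants) at baseline, 6, 12 and 18 months" and is named among the mixed-model covariates. If such terms are used, or hospital data are incomplete, the degrees of freedom need reducing.

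Restate the hospital-level power in Sample Size for the chosen test, with its inputs.

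The drafting cost is a sentence or two and an analysis option. The statistical cost is real: intervals are 2.228/1.789 = 1.245 times as wide as uncorrected ones. An effect with .90 power under the uncorrected test has about .80 with the corrected single contrast, and about .58 in the joint case.
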